17.9.3 Demographic and Other Baseline Variables

Demographic and baseline condition related characteristics will be tabulated. Continuous variables will be summarized by a mean, standard deviation, minimum, median, and maximum, and categorical variables by a count and percentage.

17.9.4 Disposition of Subjects

Treatment tolerability will be presented by treatment groups, the number and percent of subjects who fail to complete the study and the number and percent of subjects who fail to complete the study because of Adverse Events will be presented. Time to withdrawal will also be assessed and presented by Kaplan-Meier curves and will be compared using the Log-Rank test if relevant.

17.9.5 Efficacy Analysis

Doc No: 280CLD Rev: 01 Date: 24 May 2021

Page 73 of 103

The subject's CSBM1 success status (i.e. if the subjects achieve an increase from baseline of at least 1 weekly CSBM during at least 6 out of the 8 treatment weeks) will be presented in tabular form by study arm, along with 95% Wilson score Confidence Intervals (CI) and will be compared between the study arms with a Cochran-Mantel-Haenszel test controlling for center.

The CSBM2, the expanded CSBMs and the SBM success rates will be analyzed in a similar manner.

The incidence of rescue medication and the rate of SBM within 24 hours from the first study dose use will be analyzed in a similar manner.

The change from baseline in average straining will be modeled with an Analysis of Covariance (ANCOVA) model, with baseline average straining and site entered as covariates. The adjusted means of the change from baseline per study arm, and the difference between the groups will be presented along with respective 95% CI. The change from baseline in average stool consistency, in average bloating, in weekly number of SBM and CSBM, and in symptoms will be analyzed with similar ANCOVA models.

Time to occurrence of SBM after intake of the first Vibrant capsule (either active or placebo) will be assessed and presented by Kaplan-Meier curves and will be compared between the study arms using the Log-Rank test if relevant.

Treatment satisfaction, and incidence of use of rescue medication will be presented in tabular form.

The PAC-QoL, the rescue medication use, and the rate of SBM during the first 24 hours after the first dose will be presented in tabular form.

17.9.6 **Treatment by Center Interaction**

Poolability will be tested in the primary analysis at a significance level of 10%.

Poolability across centers, for the primary endpoints, will be assessed using a logistic regression model.

Centers will be grouped together by geographical area, a table of the sites and their geographical area within and without the USA will be presented. If found significant, the reason for the significance would be further explored and rationalized. This evaluation may include demographic features, symptoms at presentation, clinical and treatment history, and site comparability in the features found to be associated with the primary performance variable.

Doc No: 280CLD	
Rev: 01	Date: 24 May 2021
Page 74 of 103	

Pooling analysis will be repeated with US centers combined, and Out of US (OUS) centers combined.

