17.4 Sample size

A sample size is calculated to test the null hypotheses. Calculations (using SAS® proc power) show that a sample size of 92 subjects (46 in each study arm), would provide 80% power at a study wise 5% level of significance (two-sided), i.e., 2.5% for each one of the primary endpoints to detect a difference of 28% in the success rate, assuming a success rate of 12% in the placebo arm.

The sample size will be increased to at least 102 subjects (51 in each study arm) to account for a potential 10% of drop-out rate.

Doc No: 280CLD

Rev: 01 Date: 24 May 2021

Page 68 of 103

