17.5.3 Decision Rules

The purposes of the interim analysis is to re-assess the sample size based on conditional power

The study will either continue to the originally planned sample size if the result is "favorable", stop for futility if the result is "unfavorable", or an increase will be made to the sample size if the result is "promising". These decisions will be made based on the

Page 69 of 103

conditional power (CP), defined as the conditional probability that the result will exceed a critical value at the interim given the observed effect size $\widehat{\delta_1}$ = difference between CSBM success rates active versus placebo at the interim look. Notation:

n1= sample size at interim analysis (40 subjects in each study arm).

n2= original sample size calculated based on assumed effect size (92).

nmax = the highest sample size the company is willing to use, <math>nmax = 250 (including allowance for drop-out).

CPmin=is the calculated minimum CP based on the ratios nmax/n2, n1/n2 and the target study power (80%).

The following are the decision rules for the interim analysis. These depend on the zone into which CP falls at the interim, the calculated CPmin, the maximum sample size designated for the study and the % of the originally planned sample size at which the interim analysis will be performed. Following this principle does not inflate the Type I error.

- 1. If the respective conditional power for each of the primary endpoints is < 25.78or if the difference between the success rate (treatment –placebo) for both primary endpoints is less than 10%, then stop the trial for futility.
- 2. a. If the conditional power for both primary endpoints is 25.78≤ CP < 80% then recalculate the sample size to recover the targeted 80% for both endpoints, the maximum sample size selected will be the larger of the two.
 - b. If the CP of only one of the primary endpoints is $25.78 \le CP \le 80\%$ then recalculate the sample size to recover the targeted 80% for that endpoint alone.
 - In both cases a and b, the maximum sample size for the study will be 250 subjects
- 3. If the respective conditional power for each of the primary endpoints is $\geq 80\%$ then continue to the originally planned sample size. Note that the interim analysis will be conducted on both the ITT and mITT analysis sets, and the study will be stopped due to futility only if the interim effects in both populations fall below the threshold.

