17.8.5 Statistical Analysis of Analysis Sets

The SA analysis set will serve as the main set for safety assessments.

The mITT analysis set will serve as the main set for efficacy assessments.

The efficacy assessment will be presented on the ITT and PP analysis sets.

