17.9.8 Handling of Missing Data

Subjects with less than 6 weeks of diary data will be considered as failures for the CSBM and SBM success rates, as the primary imputation method for missing data.

Additional sensitivity analysis of the primary end-point will be performed to assess the impact of missing data on the study outcome using possible imputation methods for binary data:

- Multiple imputation for binary data.
- Observed Data: Use only subjects with 8 weeks of non-missing diary data and who did not withdraw early from study.
- Best Case Scenario: Assume all subjects with missing data in study group are successes; Assume all subjects in the placebo group with missing data are failures.
- Worst Case Scenario: Assume all subjects with missing data in study group are failures; Assume all subjects in the placebo group with missing data are successes.

In addition, for missing diary day, the number of bowel movement will be imputed to "0", and the intake of rescue medicine to "No". For the time to first SBM analysis, subjects with no known SBM will be considered left censored.

For the analyses of the other endpoints, no imputations for missing values will be performed.

Doc No: 280CLD

Rev: 01 Date: 24 May 2021

Page 75 of 103

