28. SUBJECT / STUDY DISCONTINUATION

Page 81 of 103

Subjects should be removed from the study whenever considered necessary for their welfare or when the subject expresses a desire to withdraw from the study. Non-compliance with the protocol, the occurrence of a Serious Adverse Event or any medical condition that, in the opinion of the investigator, warrants discontinuation from the study for the safety of the subject, may necessitate discontinuing a subject. If a subject is discontinued, the reason must be entered on the case report form and signed by the investigator. In case of any questionable situation, the study monitor or Vibrant Ltd. personnel should be consulted. When a subject is removed from the study as a result of Serious Adverse Event, a final physical examination must be performed. Subjects removed from the study because of an adverse event will be followed-up until the adverse event has been resolved.

In the case that the occurrence of adverse events is greater than anticipated, the clinical investigation will be suspended; in such a case, a safety committee will be arranged to decide if the study could be continued. The Ethics Committee will be notified and the results of the safety committee discussions will be brought for the EC/IRB review and decision.

Early termination could be a result of:

- 1. Withdrawal of informed consent by the subject.
- 2. Subjects who after inclusion develop medical diseases which may affect the function and interpretation of study results.
- 3. Serious protocol deviation.
- 4. Non-compliance with medical device administration or study procedures as determined by the sponsor.
- 5. Change in subject's condition.
- 6. Subject is Lost to follow-up.
- 7. Confirmed pregnancy.
- 8. Regulatory authorities stop the trial.

During the study, subjects exiting the trial will be replaced with new subjects, up to 10%

Site staff should set an early termination visit as soon as they become aware of subject's discontinuation. During this visit, any remaining study supplies should be collected and accountability should be conducted if applicable. 'End of study' from should be completed in source documents and any other relevant information should be documented (for example, in case of AE).

Doc No: 280CLD

Rev: 01 Date: 24 May 2021

Page 82 of 103

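### The 80% per-endpoint power in 17.4 fits an unstratified test; at the same fixed N of 92 the planned CMH by center has about 73–78% if about 30 similar centers enroll

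*Combined protocol and SAP*

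**What the plan says.** Section 17.4 states that "a sample size of 92 subjects (46 in each study arm), would provide 80% power" at a study-wise two-sided 5%, that is, "2.5% for each one of the primary endpoints to detect a difference of 28% in the success rate", with 12% success assumed on placebo. It cites SAS proc power but names no test and mentions no strata. The total is then raised to at least 102 for 10% drop-out: 51 per arm in 17.4, but 54 per arm in the synopsis.

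For the primary analysis, 17.9.5 and the synopsis say that CSBM1 success "will be compared between the study arms with a Cochran-Mantel-Haenszel test controlling for center"; CSBM2 is handled in the same way. Section 15.1 plans about 30 centers, and 17.6 stratifies randomization by center with varying block sizes that are not given. Section 17.9.6 groups centers by geographical area, but only for the poolability check by logistic regression. The areas are not listed, and nothing carries them into the CMH.

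The same 92 enters the interim rules in 17.5.3: "n2= original sample size calculated based on assumed effect size (92").

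**The concern.** A CMH test compares arms only within strata. A center whose subjects all fall in one arm contributes nothing, and a center split unevenly contributes less than its size suggests. With 92 subjects in about 30 centers (92/30 ≈ 3.1), most strata lose some information in this way. If 17.4 was calculated for a test without strata, its 80% is the power of a test other than the planned one. At stake is the accuracy of the stated power and of the 92 carried into the interim rules. The validity of the test is not in question.

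**Working it through.** **Inputs.** Success rates 12% and 40%, two-sided 2.5% per endpoint, 80% power and 46 per arm (17.4); CMH by center (17.9.5); about 30 centers (15.1); 1:1 blocks within center (17.6). Block sizes, center sizes and differences between centers are not in the documents. They are assumed and shown as ranges.

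**Step 1: reproduce the plan's figure.** Unstratified two-proportion formula without continuity correction, with p̄ = (0.12 + 0.40)/2 = 0.26:

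n = [z₀.₉₈₇₅·√(2·p̄·(1−p̄)) + z₀.₈₀·√(p₁(1−p₁) + p₂(1−p₂))]² / (p₂−p₁)²

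= [2.2414·√0.3848 + 0.8416·√0.3456]² / 0.28² = (1.3904 + 0.4948)² / 0.0784 = 45.33, so 46 per arm.

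Power at 46 = Φ[(0.28·√46 − 1.3904)/0.5879] = Φ(0.865) = 80.7%. At 51 per arm it is Φ(1.036) = 85.0%. A continuity correction would give 53 per arm and a one-sided test 38, so neither explains the 46.

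**Step 2: a hand check of the loss.** For similar centers, information is proportional to the sum over centers of a·c/n, where a and c are the numbers in the two arms. Without strata this is 46·46/92 = 23. Spread 92 subjects as evenly as possible over 30 centers (28 of 3 and 2 of 4) and split each as well as possible: 28·(2·1/3) + 2·(2·2/4) = 20.67. The ratio is 20.67/23 = 0.90, an effective 46·0.899 = 41.3 per arm, and power Φ[(0.28·√41.3 − 1.3904)/0.5879] = Φ(0.697), about 76%. One-arm centers lower this further; unequal center sizes can move it either way.

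**Step 3: simulation of the planned test** at fixed N, one endpoint, two-sided 2.5%, CMH without continuity correction, permuted blocks within center. Ranges run over blocks from {2} to {4,6}, with similar centers.

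| Setting | CMH by center | Unstratified |
|---|---|---|
| N=92, 30 centers | 73–78% | 81–83% |
| N=92, 20 centers | 77–80% | – |
| N=92, 10 centers | 81–82% | – |
| N=102, 30 centers, no loss | 80–83% | 86% |
| N=102, 30 centers, 10% drop-outs as failures | 73–77% | 80% |

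The last row uses 0.9·12% = 10.8% and 0.9·40% = 36%. With 30 centers, 80% power for the CMH needs about 97–102 evaluable subjects.

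**Step 4: type I error.** With 30 centers and a common rate of 12% or 26%, the CMH by center rejects in 1.9–2.5% of trials, against the nominal 2.5%.

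**Step 5: pooled strata and center differences** (N=92). With similar centers, four pooled strata give 81–82%. With a center logit SD of 1.0, the results are 80–84% by center and 82–83% pooled if 12% and 40% are overall rates, and 70–74% and 72–73% if they are within-center rates.

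**The case against.** The strongest objection is that a fixed-N, 2.5% calculation is not the planned decision procedure. Section 17.9.2.2 applies Benjamini-Hochberg, so both endpoints are rejected if both p-values are at most 5%, and 13.1 declares success if either endpoint wins. With an assumed CSBM2 rate of 8% against 32%, and the interim ignored, study success is 81–85% with the CMH by center. This stands: a reader might infer that the trial's chance of success falls below 80%, and the documents do not support that. The same run gives 87–88% unstratified, so the relative loss persists. Also, the 80% in 17.4 is itself a per-endpoint figure at 2.5%, so the comparison is like for like.

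Second, the interim serves to "re-assess the sample size based on conditional power" and can raise the total to 250. With this modelled for one endpoint and similar centers (interim at 80, cap of 225 evaluable, i.e. 250 less an assumed 10%), power is 75–83% by center and 84–86% unstratified. The increase recovers only part of the loss.

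Third, more than 92 may be analysed: 102 are randomized, and under section 28 "subjects exiting the trial will be replaced with new subjects, up to 10" percent. If all 102 count without loss, power is 80–83%. But the extra subjects are there for drop-out. "The mITT analysis set will serve as the main set for efficacy assessments", and within it "Subjects with less than 6 weeks of diary data will be considered as failures for the CSBM and SBM success rates". Drop-outs who stay in that set dilute the success rates.

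Fourth, randomization is stratified by center, so a CMH by center matches the design and is a legitimate choice. This also stands. The fault lies in the stated power. It is tempting to conclude that the test should be replaced by one with pooled strata, but the results under strong center differences do not support that.

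**Conclusion.** The 80% in 17.4 does not describe the planned test under the planned number of centers. On the plan's own terms (N fixed at 92, two-sided 2.5%, one endpoint), power for the CMH by center is about 73–78%, or about 2–7 points below the stated 80%. This rests on about 30 enrolling centers with similar success rates and on assumed block and center sizes. With 20 centers the shortfall is small, and with 10 it disappears. Center differences do not reliably restore 80%.

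That the 80% comes from an unstratified test is an inference, since 17.4 names no test, but the formula returns exactly 46 per arm. The documents do not support reading this as bias, as type I error inflation, or as study-wise power below 80%. Separately, the synopsis figure of 54 per arm is wrong for a total of 102, because 2·54 = 108 and 2·51 = 102.

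**What to change.** In 17.4 and the synopsis, name the test behind the 80% and restate the power. For example:

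> The 92 subjects give 80% power per endpoint for an unstratified comparison of two proportions at two-sided 2.5%. For the CMH test by center at the same fixed N and level, power is about 73–78%, assuming about 30 centers with similar success rates. The Benjamini-Hochberg procedure, the either-endpoint rule and the interim sample-size increase are not included.

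Give the assumed number of centers but not the block sizes, which should stay in a restricted document to protect allocation concealment. The cost is a few sentences.

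Optional alternative: in 17.9.5 and the synopsis, pre-specify a few listed pooled strata for the CMH, fixed before any unblinding, including the interim, with randomization still stratified by center. The strata must be newly defined, because 17.9.6 does not list its areas. This restores about 81–82% if centers are similar, with no extra subjects. It gains little or nothing if center success rates differ strongly, and differences within a pooled stratum are then not adjusted for.

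In either case, change 54 to 51 per arm in the synopsis.

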15.8 Run-in period (day -28 or -14, to -1)

Eligible subjects after screening, will be asked to refrain from taking any medication or supplement to relieve their constipation. Subjects will complete the eDiary every day before bedtime. Subject's eligibility according to inclusion #3 will be determined based on 14 consecutive days.

In the eDiary the subjects will be asked to report on their:

- · Daily BM,
- Change of diet, if applicable (NOTE: the protocol will not ask the patient to change anything in his/her diet. any change of diet will be recorded in the eDiary)
- Change in symptoms as: Bristol stool consistency, straining, bloating, and the other questions in the eDiary
- Medication
- change in general health condition

The run-in period may be extended by a few days in case of technical issue (difficulty to access eDiary or in case a clear decision cannot be made), to allow for a wash-out period, or other. The run-in period may be extended by up to 14 days.

In case of extension, the last 14 consecutive days of the eDiary will be monitored to determine eligibility of the subjects (based on inclusion #3). Subjects need to have an average of \geq 1 SBM and \leq 2.5 SBM per week during the two weeks of run-in for eligibility. In any case, subjects should have at least 1 SBM and not more than 3 SBMs during each of the run-in weeks.

Doc No: 280CLD

Rev: 01 Date: 24 May 2021

Page 51 of 103

The study coordinator will monitor the e-diary of each patient to confirm patient's compliance and that data entered is clear. The subjects will receive a short phone call as needed from the study coordinator.

The phone calls may include clarification re eDiary entries, resolving issues of subject compliance with the eDiary, occurrence of adverse events, use of rescue medication, subject understanding of what he/she needs to do in the context of the study and discussion of any issue or difficulty that the subject might have. Documentation of the date and time of the phone call will be reported on the eCRF.

Subjects that miss to complete 3 days (or more) of the e-diary (not due to technical issues) during the run-in period, may be considered as screening failures due to lack of compliance.

During the run in (as well as throughout the whole study period) subjects will need to adhere to rescue medication rules (see section 15.12). Subject that used 3 rescue meds (or more) during the run in period will be considered a screening failure.

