17.2 Study Endpoints

17.2.1 Primary Efficacy Endpoint

There are two primary efficacy endpoints for this study.

The two primary efficacy endpoints are the CSBM1 success rate, defined as an increase from the run-in period of at least one weekly Complete Spontaneous Bowel Movement (CSBM) during at least 6 of the 8 weeks of treatment, and CSBM2 success rate, defined as an increase from the run-in period of at least two weekly Complete Spontaneous Bowel Movement (CSBM) during at least 6 of the 8 weeks of treatment.

The study will be deemed successful if either the CSBM1 or the CSBM2 success rate is statistically significantly higher in the active arm, than in the placebo arm.

Doc No: 280CLD Rev: 01 Date: 24 May 2021

Page 66 of 103

17.2.2 **Secondary Efficacy Endpoints**

Secondary efficacy endpoints include:

- Change from baseline in average straining. 1.
- 2. CSBM1 expanded success rate, defined as an increase from the run-in period of at least one weekly Complete Spontaneous Bowel Movement (CSBM) during at least 5 of the 8 weeks of treatment.
- Change from baseline in average stool consistency, using the Bristol Stool Scale 3.
- 4. CSBM2 expanded success rate, defined as an increase from the run-in period of at least two weekly Complete Spontaneous Bowel Movement (CSBM) during at least 5 of the 8 weeks of treatment
- 5. Change from baseline in average bloating.

17.2.3 **Additional Efficacy Endpoints**

Additional efficacy endpoints include:

- SBM success rate, defined as an increase from baseline at least one weekly spontanuous Bowel Movement (SBM) during at lease 6 out of 8 weeks of treatment.
- Incidence of Rescue Medication use during the treatment period.
- Change from baseline in weekly number of Spontaneous Bowel Movement (SBM).
- Change from baseline in weekly number of Complete Spontaneous Bowel Movement (CSBM).
- Rate of SBM < 24 hours after first dose
- Change from baseline in average abdominal gas.
- Change from baseline in average abdominal pain.
- Change from baseline in abdominal discomfort.
- Time to occurrence of spontaneous bowel movement after first capsule activation.
- Change from baseline in quality of life using the PAC-QOL (Patient Assessment of Constipation Quality of Life) questionnaire.

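### The primary CMH test controls for center only; adding run-in weekly CSBM as a single covariate would be a cheap refinement worth roughly 0 to 4 points of power

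*Combined protocol and SAP*

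**What the plan says.** Section 17.9.5 (and the synopsis) states that the CSBM1 success status "will be compared between the study arms with a Cochran-Mantel-Haenszel test controlling for center". CSBM2, the expanded CSBM rates and the SBM success rate follow the same method. Randomization is stratified by center only (17.6), and about 30 centers are planned (15.1).

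The continuous endpoints are treated differently. Change in average straining is analyzed by ANCOVA "with baseline average straining and site entered as covariates". Stool consistency, bloating, weekly SBM and CSBM counts and symptoms get similar models.

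The primary endpoints are measured against run-in. In 17.2.1, CSBM1 success is "defined as an increase from the run-in period of at least one weekly Complete Spontaneous Bowel Movement (CSBM) during at least 6 of the 8" treatment weeks, and CSBM2 is the same with two. The run-in diary is completed daily, and subjects are trained beforehand on what counts as complete evacuation (15.7). If the run-in is extended, "the last 14 consecutive days of the eDiary will be monitored to determine eligibility" (15.8).

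Section 17.4 plans "a sample size of 92 subjects (46 in each study arm" group) to "detect a difference of 28% in the success rate, assuming a success rate of 12% in the placebo arm", at 2.5% two-sided for each primary endpoint.

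**The concern.** Run-in weekly CSBM is the reference for each subject's success threshold, so it is the natural candidate for a prognostic baseline variable. Neither the randomization nor the primary analysis uses it. A chance imbalance between two arms of about 46 subjects therefore stays in the estimated difference as noise. The plan already accepts adjustment of an outcome for its own baseline in the ANCOVA endpoints, but the two endpoints that decide the trial get no equivalent.

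What is at stake is precision. If run-in CSBM is associated with response in either direction, a test that uses it has somewhat more power at the same sample size and needs no new data.

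**Working it through.** **1. The plan's own figure.** Inputs from 17.4: placebo 12%, active 12% + 28% = 40%, two-sided alpha 2.5% per endpoint, power 80%. The mean rate is 0.26, z(0.9875) = 2.2414 and z(0.80) = 0.8416.

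n per arm = [2.2414·√(2·0.26·0.74) + 0.8416·√(0.12·0.88 + 0.40·0.60)]² / 0.28²
= [2.2414·0.6203 + 0.8416·0.5879]² / 0.0784 = 3.554 / 0.0784 = 45.3, rounded up to 46, so 92 in total.

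This matches exactly. Power at 46 per arm is Φ[(0.28·√46 − 2.2414·0.6203)/0.5879] = Φ(0.865) = 80.7%. The formula has no covariate and no center strata, so the stated power does not count on adjustment.

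**2. Approximate gain from one covariate.** If run-in CSBM has correlation ρ with responder status, adjustment multiplies the variance by about 1 − ρ². This is equivalent to 46/(1 − ρ²) subjects per arm. The documents do not give ρ, so it is an assumption.

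| assumed absolute ρ | effective n per arm | power | gain (points) |
|---|---|---|---|
| 0 | 46.0 | 80.7% | 0 |
| 0.1 | 46.5 | 81.1% | 0.4 |
| 0.2 | 47.9 | 82.4% | 1.7 |
| 0.3 | 50.5 | 84.6% | 3.9 |

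A gain of 5 points would need an absolute ρ of about 0.35.

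**3. Plausible ρ.** Simulated diaries with gamma-Poisson SBM rates and beta-distributed completeness, filtered by the eligibility rule (1 to 3 SBM each run-in week, mean at most 2.5), gave an absolute ρ of about 0.07 to 0.32. These distributions are assumptions.

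**4. Power of the proposed test.** CMH by center against the covariate-adjusted CMH with the same center strata, in that diary model (92 subjects, 3,000 runs, 12% vs 40%, alpha 2.5%):

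| setting | CMH | adjusted CMH |
|---|---|---|
| CSBM1, 30 centers | 77.2 / 74.4 / 76.9% | 79.3 / 77.9 / 78.3% |
| CSBM2, 30 centers | 76.1 / 74.5% | 77.0 / 75.1% |
| CSBM1, 1 center | 82.4 / 80.7 / 82.2% | 84.4 / 84.4 / 84.5% |
| CSBM2, 1 center | 81.6 / 80.5% | 82.6 / 81.0% |

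The gains are 1.4 to 3.7 points for CSBM1 and 0.5 to 1.0 point for CSBM2. One CSBM2 case with 10 centers went the other way (80.2% vs 79.5%). A single estimate has a standard error of about √(0.8·0.2/3000) = 0.7 point. Null rejection was 0.018 to 0.029 for both tests.

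A second simulation used a logistic link, permuted blocks by center and 4,000 runs. With 30 centers it gave 76.5 vs 76.8% (ρ = −0.14), 76.2 vs 78.1% (ρ = −0.23) and 76.9 vs 79.4% (ρ = +0.29), so the gain appears for either sign. Null rejection was 0.019 to 0.024. With a covariate unrelated to response, power fell by 0.7 point (75.8 to 75.1%; 81.0 to 80.3%).

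**5. The obvious alternative.** Making run-in CSBM (0 vs above 0) an extra CMH stratum gives up to 30 × 2 = 60 strata for 92 subjects, or about 1.5 per stratum. Simulated power with 30 centers then falls from about 76% to about 60–64%. The route matters.

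**The case against.** The case for leaving the plan alone is substantial, and most of it stands.

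- **Nothing is wrong with the planned test.** It matches the stratified randomization, is unbiased, and already allows for chance imbalance through its type I error. N = 92 stands without adjustment.
- **A loss of power is not demonstrated.** A reader might infer that run-in CSBM must be prognostic because it sets the threshold. The endpoint is already an increase over run-in, eligibility narrows the range (weekly SBM averages at most 2.5), and severity and threshold effects could offset each other. The documents give no correlation.
- **The plan is not inconsistent about this variable.** A reader might infer that run-in CSBM is adjusted for in the secondary analyses. It is not. Straining, consistency and bloating use their own baselines, and the two expanded rates use the same center-only CMH. Baseline CSBM enters only the model for weekly CSBM count, which 17.2.3 lists as an additional endpoint.
- **The reference value is undefined.** It is tempting to argue that a 14-day mean moves in halves, so that a subject with 0.5 at run-in needs 2 CSBM in a week. The averaging in 15.8 concerns SBM eligibility, 17.9.1 defines baseline as the last valid value before treatment, and no section defines the run-in CSBM value.
- **The interim is affected.** Section 17.5 says the final analysis uses the conventional test, and 17.5.3 bases conditional power on the observed difference in success rates. The simulations fix N at 92 and do not test type I error under a sample-size increase.
- **A larger loss lies elsewhere.** Under assumed center sizes, stratifying 92 subjects over 30 centers takes power from about 81% to about 76%. The loss is 2 to 3 points with 20 centers and about 1 point or less with 10. Covariate adjustment only partly offsets it.

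These points limit the claim to efficiency. They do not remove it: the covariate is already collected, the adjusted test held its size at fixed N, and the possible loss is smaller than the plausible gain for CSBM1.

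**Conclusion.** The point holds as an optional efficiency improvement of low severity. The primary test omits a collected baseline value that is the reference for its own endpoint. Under an assumed absolute correlation of about 0.1 to 0.3, using it would add roughly 0 to 4 points of power, and about 1 point or less for CSBM2. If run-in CSBM is not prognostic, up to about 0.7 point could be lost.

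The size rests on assumed diary distributions and center sizes, because the documents report no association between run-in CSBM and response. The documents do not support reading the omission as a bias, an inflated type I error or a fault in the sample size.

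**What to change.** Before unblinding, and before the interim:

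1. In 17.2.1 and 17.9.1, define the run-in weekly CSBM value used for the endpoint (which days, and whether a mean), and use that value as the covariate.
2. In 17.9.5, keep the center strata and add this single covariate through the stratified randomization-based (nonparametric ANCOVA) CMH for CSBM1, CSBM2 and the expanded rates. For center h let w_h = n_h1·n_h0/n_h. Let d_y and d_x be the sums over centers of w_h times the between-arm difference in mean response and in mean run-in CSBM. Let V_yy, V_yx and V_xx be the sums of w_h times the within-center variances and covariance. The statistic is (d_y − V_yx·d_x/V_xx)² / (V_yy − V_yx²/V_xx), referred to chi-square with 1 df. Without x it is the planned CMH.
3. State that run-in CSBM is not to be used as an additional CMH stratum.
4. Report the unadjusted CMH as a sensitivity analysis.
5. In 17.5 and 17.5.3, base conditional power on the same adjusted statistic, and check type I error by simulation with the sample-size increase included.

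The cost is SAP wording, a few lines of code and minor alignment of the interim text, with no new data or subjects. The downsides are a less familiar primary test and the possible loss of up to about 0.7 point of power.
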